#### **9.1.6 Follow-up of Adverse Events and Serious Adverse Events**

After the initial AE/SAE report, the investigator is required to proactively follow each participant at subsequent visits/contacts. All AEs and SAEs will be followed until resolution, until the condition stabilizes, until the event is otherwise explained, or until the participant is lost to follow-up.

#### **9.1.7 Reporting of Serious Adverse Events**

All new SAEs must be reported in English to the Project Management Board within 24 hours of the investigator's first knowledge of the event regardless of relationship to the study procedures. All deaths must be reported within 24 hours of the investigator's first knowledge of the event. It is recognized that complete information may not be available at the time of the initial SAE report. Additional information should be supplied on subsequent Serious Adverse Event Forms as it becomes available.

For the initial SAE notification report, the investigator must provide, at minimum, basic information such as the protocol number, participant's initials and date of birth, participant identification number, period of investigational product intake, event term, nature of the event, the seriousness criteria, and the investigator's attribution regarding relatedness to investigational product. In addition, the initial SAE report should

include all pertinent known information about the SAE and the affected participant. In addition, the investigator should provide a narrative to describe the course of events including any treatments or relevant procedures. Follow-up information, which may include copies of relevant participant records and other documents not available at the initial SAE report must be sent to the Project Management Board as soon as available. Follow-up SAE reports may describe the evolution of the reported event and any new assessment of outcome and/or relationship to investigational product. Full supporting documentation should be solicited by the investigative site even if the SAE occurred at another institution. Such documentation may include copies of relevant medical/hospital records, pathology, or autopsy reports where available.

#### ***9.1.8 Regulatory Reporting Requirements for Serious Adverse Events***

Prompt notification by the investigator to the medical supervisor of all SAEs and non-serious AEs occurring during a clinical trial is essential so that legal obligations and ethical responsibilities towards the safety of participants are met.

An investigator who receives an investigator safety report describing an SAE(s) or other specific safety information (e.g., summary or listing of SAEs) will file it with the Investigator Brochure and will notify the Institutional Review Board/Institutional Ethics Committee (IRD/IEC), if appropriate according to local requirements.

---

## 10 Data Management

### 10.1 Site specific

Each site PI is responsible for the management and storage of data collected at the site. All data will be collected using standard de-identification procedures:

1. Each participant will be allocated a unique identifier code
2. A master key matching the identifier code to the identity of the participant will be retained as a secured, encrypted data file; separate in location to all data collected in this study. The master key file can only be accessed by the site PI and authorized research personnel at the site.
3. All data collected from each participant will be identified only by the unique identifier code.
4. Data storage and security is the responsibility of the site PI
5. The site PI will transfer de-identified data to the study coordinator using secure, encrypted HTTPS transfer protocol. Only de-identified data can be transferred to the study coordinator for combining with data from all study sites to enable data analysis.
- 6.

### 10.2 Project wide

The study coordinator is responsible for the management and storage of multi-site de-identified data collected across the multiple sites involved in the RCT.

1. Data from each participant will only be identified by a unique identifier code indicating the study site from which the data was collected
2. No persons will be able to identify the identity of the individual from the identifier code used. Only the site PI will retain the master key for participant identities specific to their site.
3. Data storage and security of the combined multi-site data is the responsibility of the study coordinator

## 11 Responsibilities

### 11.1 Investigator Responsibilities

#### 11.1.1 *Good Clinical Practice*

The investigator will ensure that this study is conducted in accordance with the principles of the National Health and Medical Research Council (NHMRC) of Australia, as well as the “Declaration of Helsinki” (as amended in Edinburgh, Tokyo, Venice, Hong Kong, and South Africa), International Conference on Harmonisation (ICH) guidelines, or with the laws and regulations of the country in which the research is conducted, whichever affords the greater protection to the study participant. The investigator will ensure that the basic principles of “Good Clinical Practice,” as outlined in 21 Code of Federal Regulations (CFR) 312, subpart D, “Responsibilities of Sponsors and Investigators,” 21 CFR, part 50, 1998, and 21 CFR, part 56, 1998, are adhered to. These standards are consistent with the requirements of the European Community Directive 2001/20/EC, which shall be adhered to fulfil the contractual requirements of this European Commission funded research project.

#### 11.1.2 *Institutional Review Board/Independent Ethics Committee Approval*

This protocol and any accompanying material to be provided to the participant and caregiver (such as advertisements, participant information sheets, or descriptions of the study used to obtain informed consent) will be submitted by the investigator to an IRB or IEC. Approval from the IRB or IEC must be obtained before starting the study and should be documented in a letter to the investigator specifying the protocol number, protocol version, protocol date, documents reviewed, and date on which the committee met and granted the approval.

Any modifications made to the protocol or other documents described in the above paragraph after receipt of IRB or IEC approval must also be submitted to the IRB or IEC for approval before implementation.

#### 11.1.3 *Informed Consent*

The investigator is responsible for obtaining written informed consent from each individual participating in this study after adequate explanation of the aims, methods, objectives, and potential hazards of the study and before undertaking any study-related procedures. The investigator must utilize an IRB- or IEC-approved consent form for documenting written informed consent. Each informed consent will be appropriately signed and dated by the participant or the participant’s legally authorized representative and the person obtaining consent. Consent from both the caregiver representative and participant will be obtained.

#### 11.1.4 *Inspections*

The investigator should understand that source documents for this trial should be made available to IRBs or IECs, or to regulatory authority or health authority inspectors.

### ***11.1.5 Protocol Compliance***

The investigator is responsible for ensuring the study is conducted in accordance with the procedures and evaluations described in this protocol.

### ***11.1.6 Study Report and Publications***

A clinical study report will be prepared and provided to the regulatory agencies.

## **11.2 Joint Investigator/Consortium Responsibilities**

### ***11.2.1 Access to Information for Monitoring***

In accordance with ICH Good Clinical Practice (ICH GCP) guidelines, the Study Coordinator must have direct access to the investigator's source documentation in order to verify the data recorded for consistency.

The Study Monitor is responsible for routine review of the data collected at regular intervals throughout the study to verify adherence to the protocol and the completeness, consistency, and accuracy of the data being entered on them. The monitor should have access to any de-identified participant records needed to verify adherence. The site PI agrees to cooperate with the study coordinator to ensure that any problems detected in the course of these monitoring visits are resolved.

### ***11.2.2 Study Discontinuation***

The Consortium reserves the right to terminate the study at any time. Should this be necessary, both parties will arrange discontinuation procedures and notify the appropriate regulatory authority(ies), IRBs, and IECs.

#### **Appendix 4. Screening Assessment Checklist**

# My-AHA PARTICIPANT SCREENING ASSESSMENT PACKAGE

To be completed by Investigator interview of potential participant:

1	Date of Birth	DD / MM / YYYY	
2	Age (years)		If 60 years or older proceed If <60 yrs - EXCLUDE
3a	Able to stand and walk unassisted	YES / NO	If YES – proceed If NO - EXCLUDE
3b	Painful arthritis, spinal stenosis, amputation, or painful foot lesions that limit balance and mobility.	YES / NO	If YES – EXCLUDE If NO - proceed
4a	suffers from a significant neurodegenerative CNS disorder, e.g. Alzheimer's disease, Lewy body dementia, Frontotemporal Lobar Degeneration, Fronto-Temporal Dementia, Parkinson's disease, multiple sclerosis, progressive supranuclear palsy, amyotrophic lateral sclerosis, hydrocephalus, Huntington's disease, prion diseases	YES / NO	If YES – EXCLUDE If NO - proceed
4b	affected by severe peripheral nervous system and/or neuromuscular disorders, e.g. CIDP, myasthenia gravis, multiple sclerosis, polymyositis	YES / NO	If YES – EXCLUDE If NO - proceed
5a	clinical evidence or history of stroke (within 2 yrs)	YES / NO	If YES – EXCLUDE If NO - proceed
5b	clinical evidence or history of transient ischemic attack (within 6 months)	YES / NO	If YES – EXCLUDE If NO - proceed
5c	significant head injury with associated loss of consciousness, skull fracture or persisting cognitive impairment (2 years)	YES / NO	If YES – EXCLUDE If NO - proceed
5d	epilepsy (a single prior seizure is considered acceptable)	YES / NO	If YES – EXCLUDE If NO - proceed
5e	if meet DSM-5 criteria for: major depressive disorder (current), schizophrenia or other psychotic disorders (lifetime), bipolar disorder (within the past 5 years), substance (including alcohol) related disorders (within the past 2 years)	YES / NO	If YES – EXCLUDE If NO - proceed
6a	have language deficits that impair testing	YES / NO	If YES – EXCLUDE If NO - proceed
6b	have significant visual impairment	YES / NO	If YES – EXCLUDE If NO - proceed
6c	have a significant hearing loss	YES / NO	If YES – EXCLUDE

# My-AHA PARTICIPANT SCREENING ASSESSMENT PACKAGE

			If NO - proceed
7a	have clinically significant cardiovascular disease, i.e: hospitalization for acute coronary syndrome (acute myocardial infarction or unstable, angina), symptoms consistent with angina pectoris (within the 12 months), signs or symptoms of clinical heart failure within the 12 months, evidence of uncontrolled atrial fibrillation, a cardiac pacemaker	YES / NO	If YES – EXCLUDE If NO - proceed
7b	preexisting or current signs or symptoms of respiratory failure, e.g. chronic obstructive pulmonary disease, bronchial asthma, lung fibrosis, other respiratory disease	YES / NO	If YES – EXCLUDE If NO - proceed
7c	untreated hypertension	YES / NO	If YES – EXCLUDE If NO - proceed
7d	metastatic cancer or immunosuppressive therapy	YES / NO	If YES – EXCLUDE If NO - proceed
7e	concurrent acute or chronic clinically significant immunologic, hepatic (such as presence of encephalopathy or ascites), or endocrine disease (not adequately treated).	YES / NO	If YES – EXCLUDE If NO - proceed
8	Prescription medication other than for treating conditions in 3b to 7e		Confirm participant can proceed into RCT with medical monitor if other medications are reported
9	Postural hypotension at the time of screening.	BP sitting Sys = _____ Dias = _____  BP standing Sys = _____ Dias = _____	Standing systolic BP >30mgHG lower than sitting systolic BP - EXCLUDE and/or Standing diastolic BP >20mmHg lower than sitting diastolic BP - EXCLUDE  If does not meet above - proceed
10	Legally able to consent	YES / NO	If YES – proceed If NO - EXCLUDE
11	Gender	Male / Female	
12	Height	_____ m	

# My-AHA PARTICIPANT SCREENING ASSESSMENT PACKAGE

13	Weight	_____ kg
14	BMI	_____ [height(m)/weight (kg)] / [height(m)]
15	Able to use smartphone and/or tablet computer	If YES – proceed If NO – EXCLUDE
15a	Owns own smartphone/tablet computer	YES / NO Model: _____ OS: Android / Win / Mac
15b	Has existing mobile plan and provider?	YES / NO Provider: _____ Data/mth: _____
15c	Has WiFi access at place of residence?	YES / NO
15d	Has existing internet provider and plan?	Provider: _____ Data/mth: _____

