**Table 2: Pre-frail inclusion criteria for participant screening**

Clinical sign/symptom	Measure	Cutoff values			
PHYSICAL DOMAIN					
Pre-frail = 1 or 2 of the following criteria are met					
1. Shrinking, evidenced by weight loss (unintentional)	$\geq 4.5$ kg unintentional in prior 12 months; or at follow-up assessment $\geq 5\%$ of body weight in prior 12 months	Self-reported weight loss (not due to dieting or fasting) in preceding 12 mo $\geq 4.5$ kg Follow-up: $K = (\text{weight in previous year} - \text{current measured weight}) / (\text{weight in previous year})$ . If $K \geq 0.05$ , meets weight loss frailty criteria			
2. Weakness	Grip strength in lowest 20% at baseline adjusted for gender and BMI	BMI Men BMI $\leq 24$ Men BMI 24.1 - 26 Men BMI 26.1 - 28 Men BMI $> 28$  Women BMI $\leq 23$ Women BMI 23.1 - 26 Women BMI 26.1 - 29 Women BMI $> 29$	Grip strength cutoff (kg) $\leq 29$ $\leq 30$ $\leq 30$ $\leq 32$  $\leq 17$ $\leq 17.3$ $\leq 18$ $\leq 21$		
3. Poor endurance and energy	Self-report of exhaustion as indicated by responses to 2 questions on CES-D scale	Using the CES-D Depression Scale, response of “2” (a moderate amount of the time, 3-4 days) or “3” (most of the time) to either of the following 2 items: (a) I felt that everything I did was an effort; and/or (b) I could not get going.			
4. Slowness	Time to walk 15ft (4.57m) $\leq$ slowest 20% adjusted for gender and standing height	Gender/Height (cm) Men Height $\leq 173$ cm Men Height $> 173$ cm Women Height $\leq 159$ cm Women Height $> 159$ cm	Cutoff time to walk 4.00 m) $\geq 6.13$ sec $\geq 5.25$ sec $\geq 6.13$ sec $\geq 5.25$ sec		

5. Low physical activity level	Energy expenditure per week below established cutoff	Short version of the IPAQ questionnaire assesses activity levels for walking, moderate-intensity and vigorous-intensity activities for work, transportation, domestic chores, gardening and leisure-related activities.	IPAQ Activity level measures as MET-min units). Convert IPAQ Met-min units to kcal using following formula adjusting for participants weight in kg: $[\text{kcal} = \text{MET-min} \times (\text{weight kg}/60)]$ Gender specific cutoff values: 
 
▪ Men: < 383 kcal
 
▪ Women: <270 kcal
 

---------------------------------------	--	---	--

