**Figure 2: Schematic of Study Design**

**Table 6: Assessment battery for the My-AHA RCT assessment points**

DOMAIN	Test name	Screening	Baseline	6mth	12mth	18mth
Consent process	Information sheets and consent forms (Appendix 1, Appendix 2, Appendix 3)	✓ Appendix x 1	✓			
Screening questionnaire	Screening for inclusion and exclusion criteria; including pre-frail assessment	✓				
Demographic	Standard questionnaire 
 
• Date of birth
 
• Gender
 
• Education (years completed)
 
• Residential status (live alone, with other etc.)
 
• Fear of falls
 
• Falls history
 
• Cognitive activities (mental activity)
 
• Medical history (diseases/diagnoses past and current, medication history)
 
• Continence
 
		✓			
	Brief demographic update questionnaire (to track demographic variables than can change over time): 
 
• Change in residential status since prior assessment
 
• Fear of falls
 
• Falls history since previous assessment
 
• Continence
 
• Cognitive activities (mental activity) since previous assessment
 
• Medical since previous assessment point (diagnoses existing and new, medication prescription current)
 
			✓	✓	✓
RCT Adherence	Cognitive games (in My-AHA platform) time spent in game, time scheduled	✓	✓	✓	✓	
	iStoppFalls – time spent/time scheduled	✓	✓	✓	✓	
	FAME – calendar with diary	✓	✓	✓	✓	
	OTAGO – calendar with diary	✓	✓	✓	✓	
	Endurance training (heart rate monitor, calendar with diary)	✓	✓	✓	✓	
	VitalinQ – time spent/recipes used	✓	✓	✓	✓	
	Technology – duration and frequency of app use	✓	✓	✓	✓	
Health	WHO-QoL OLD	✓	✓	✓	✓	
	Lawton-Brody iADL scale	✓		✓	✓	
Physical	Weight (kg)	✓	✓	✓	✓	✓
	Height (cm)	✓	✓	✓	✓	✓
	Grip strength	✓	✓	✓	✓	✓
	CES-D (2 items assessing exhaustion)	✓	✓	✓	✓	✓
	Time to walk 4m (SPPB)	✓	✓	✓	✓	✓
	IPAQ-Short version	✓	✓	✓	✓	✓

	6-minute walk test	✓	✓	✓	✓
	Short Physical Performance Battery (SPPB)	✓	✓	✓	✓
	Dual-Task Performance (repeat of gait speed test of the SPPB)	✓	✓	✓	✓
	Timed up and Go test	✓	✓	✓	✓
	ABC (self-efficacy for physical function)	✓	✓	✓	✓
	PACES (Physical Activity Enjoyment Scale)				✓
Cognitive	MMSE	✓	✓	✓	✓
	HVLT	✓	✓	✓	✓
	WMS-III Spatial Span (SSP)	✓	✓	✓	✓
	Trail Making Test (TMT-A & TMT-B)	✓	✓	✓	✓
	Stroop test (24 item Victoria Version)	✓	✓	✓	✓
	WAIS-III Digit Symbol substitution (DSS)	✓	✓	✓	✓
Psychological	HADS	✓	✓	✓	✓

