## 6.2 Screening questionnaire

Persons expressing an interest in participating in the My-AHA RCT will undergo formal screening to ensure that they meet inclusion criteria and do not meet any of the identified exclusion criteria (see Section 3 Participant Screening, Table 1, Table 2, Table 3, Table 4). A standard questionnaire for participant screening will be used (Appendix 4) along with standard forms for the MMSE, HVLT, IPAQ, and HADS which will be administered to confirm each participant meets pre-frailty criteria for inclusion in the RCT. It is estimated that the screening process will take a maximum of 60 minutes to complete.

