### **6.6.8 *Short Physical Performance Battery (SPPB)***

Equipment required:

- Chair with arms (46-18 cm high)
- Stopwatch
- Tape measure
- tape to mark 4m

SBBP subtests are administered in the following order (Appendix 10).

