## 6.10 Nutrition

### 6.10.1 BMI

The Body Mass Index (BMI) for each participant will be calculated from weight and height data collected at each assessment phase using the following formula:

$$\text{BMI} = [\text{height(m)} / \text{weight (kg)}] / [\text{height(m)}]$$

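### The BMI formula is printed as 1/weight in two places, and the screening form scores a 15 ft walk where the schedule sets a 4 m walk, so the weakness or slowness criterion can be mis-scored at eligibility

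*Protocol*

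**What the plan says.** **BMI.** Section 6.10.1 states that BMI "will be calculated from weight and height data collected at each assessment phase using the following formula", and the expression that follows is height over weight, divided by height. Item 14 of the Appendix 4 screening form repeats it: "height(m)/weight (kg)] / [height(m". BMI then enters the weakness criterion of Table 2, "Grip strength in lowest 20% at baseline adjusted for gender and BMI", whose bands split at 24, 26 and 28 for men and 23, 26 and 29 for women. The form reproduces the same bands.

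**Walking distance.** Table 2 names the slowness measure as "Time to walk 15ft (4.57m") but heads its cut-off column "Cutoff time to walk 4.00 m", with limits of 6.13 s and 5.25 s by height band. Table 6 lists "Time to walk 4m (SPPB") at all five assessments, screening included. Section 6.6.8 lists "tape to mark 4m" among the equipment, and Section 6.6.8.2 describes a 4 m course. For screening, Section 6.2 says: "A standard questionnaire for participant screening will be used (Appendix 4"). That form scores a 15 ft walk against 7 s and 6 s.

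**Eligibility.** Both Table 2 and the form require one or two of the five physical criteria. The form excludes anyone with none or with more than two.

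**The concern.** These are not background details. The BMI expression and the walking cut-offs decide two of the five yes/no answers that define the trial population, and the eligibility window is narrow on both sides.

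- Losing a YES admits a person who meets three criteria, and excludes a person whose only criterion was the lost one.
- Gaining a YES does the reverse: a person with none is admitted and a person with two is excluded.

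The two faults touch different criteria (BMI affects weakness, distance affects slowness), so each alone can flip one answer and both together could flip two. With 25 participants per arm, each misclassified enrollee is 1/25 = 4% of an arm.

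The BMI expression is meant for every assessment phase, not only screening. The form conflict is confined to screening. It could still carry forward: a person scored as not slow at screening and as slow later on the 4 m cut-offs would gain a criterion with no change in walking speed. Section 7 treats development of frailty as an adverse endpoint and gives controls who reach it access to intervention, so an artificial gain would matter there too.

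**Working it through.** **1. The printed BMI expression.** (h/w)/h = 1/w, where h is height in m and w is weight in kg.

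- 45 kg: 1/45 = 0.022
- 75 kg: 1/75 = 0.013
- 120 kg: 1/120 = 0.008

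None of these is on the 23 to 29 scale of the grip bands. Weight/height² is: at 1.60 m and 75 kg, 75/1.60² = 29.3. The Self-MNA chart in Appendix 23 implies the same definition: at 1.60 m its boundaries of 48.6, 53.8 and 58.9 kg give 19.0, 21.0 and 23.0.

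**2. Effect on the grip cut-off if the expression is used literally.** Everyone falls in the lowest band.

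| Sex, true BMI band | Table 2 cut-off (kg) | Cut-off applied (kg) | Too low by (kg) |
|---|---|---|---|
| Men ≤24 | 29 | 29 | 0 |
| Men 24.1–28 | 30 | 29 | 1 |
| Men >28 | 32 | 29 | 3 |
| Women ≤23 | 17 | 17 | 0 |
| Women 23.1–26 | 17.3 | 17 | 0.3 |
| Women 26.1–29 | 18 | 17 | 1 |
| Women >29 | 21 | 17 | 4 |

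Example: a woman of 1.60 m and 75 kg with a grip of 19 kg has BMI 29.3 and a cut-off of 21 kg, so she meets the criterion. With the printed expression her BMI is 0.013, the cut-off is 17 kg, and she does not.

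**3. The two sets of walking cut-offs agree with each other.** Scaling the form's 15 ft limits to 4 m:

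- 7 × 4/4.57 = 6.13 s
- 6 × 4/4.57 = 5.25 s

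These are Table 2's values. In speed, 4.57/7 = 4/6.13 = 0.653 m/s and 4.57/6 = 4/5.25 = 0.762 m/s.

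**4. What happens when distance and cut-off are crossed.**

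- A 4 m time on the 15 ft form: the thresholds become 4/7 = 0.571 and 4/6 = 0.667 m/s, lower by 1 − 4/4.57 = 12.5%. Times from 6.13 to just under 7 s (0.87 s wide) and from 5.25 to just under 6 s (0.75 s wide) are missed.
- A 15 ft time on Table 2's 4.00 m column: the thresholds become 4.57/6.13 = 0.746 and 4.57/5.25 = 0.870 m/s, higher by 4.57/4 − 1 = 14%. Times in the same ranges are wrongly counted as slow.

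Example A: a man of 173 cm or less walking at 0.60 m/s takes 4/0.60 = 6.67 s over 4 m. That is YES on Table 2 (≥6.13 s) and NO on the form (≥7 s). Over 15 ft he takes 4.57/0.60 = 7.62 s, which is YES on the form.

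Example B: a woman taller than 159 cm walking at 0.80 m/s takes 4.57/0.80 = 5.71 s over 15 ft. That is NO on the form (≥6 s) and YES on Table 2 (≥5.25 s). Over 4 m she takes 5.00 s, which is NO on Table 2.

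**The case against.** The strongest reply is that neither fault need do harm. A BMI of 0.013 set beside bands in the twenties is plainly absurd, so staff would notice it or would compute BMI conventionally anyway. Height and weight are recorded on the same form, so the value can be recovered. Even a literal reading affects only people whose grip lies in a strip at most 3 or 4 kg wide, and nobody in the lowest BMI band. On the walk, the form is consistent within itself, Table 2's limits are an exact conversion, and an error requires someone to disregard the distance printed above the cut-offs.

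All of this is factually right, and it limits the severity. It does not remove the contradiction. The formula is wrong in both places where it appears. On the walk, the only gait-speed procedure the protocol describes is over 4 m, and the only screening form it mandates has 15 ft limits. Staff who follow both instructions arrive at the crossed reading, so it does not depend on carelessness alone.

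**Conclusion.** The concern holds and should be fixed. The BMI expression is wrong as printed in both Section 6.10.1 and Appendix 4. The walking distance at screening is contradictory between Table 6 and the form, with both distances in Table 2.

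The size is conditional. If BMI is used literally, the grip cut-off is too low by 0 to 3 kg in men and 0 to 4 kg in women. If walk time and cut-off are crossed, the slowness threshold moves down 12.5% or up 14%. There is no error when BMI is computed conventionally and each set of walking cut-offs is used on its own distance. The protocol gives no BMI, grip or gait distribution, so the number of people affected cannot be estimated.

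The possible effect on later frailty status rests on a further assumption: that frailty means more than two criteria, as the form's exclusion rule implies. The 4 m walk at baseline might expose a screening discrepancy, but no recheck of eligibility is stated.

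**What to change.** 1. Print BMI = weight (kg) / [height (m)]² in Section 6.10.1 and in item 14 of the Appendix 4 form.
2. Reconcile Table 2, Table 6, Section 6.6.8 and item 4 of the form's physical frailty section to a single walking distance. Change label and cut-offs together, and use that distance at screening and every later visit. The choice of distance is for the investigators.
3. If anyone has already been screened, recalculate BMI from the height and weight in items 12 and 13, and re-derive slowness wherever the distance actually walked is known.

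The cost is small: one formula in two places, one label or column heading in Table 2, and one item on the form. BMI is fully recoverable; slowness is recoverable only where the distance was recorded or can be established. The drawback is that re-derivation could change the eligibility status of someone already screened.
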